#### **Small Pouch Gastric Bypass**

Our model will include patients having robotic assisted gastric bypass. Briefly, the procedure involves the placement of 6 total trocars. Two large trocars (12 mm port placed 3 cm cephalad to the umbilicus and a 12 mm port in the right mid clavicular line) undergo fascial closure at the completion of the case. The dissection is started by making a small proximal gastric pouch with a linear stapler. A hand sewn gastrojejunostomy is then created approximately 50 cm distal to the ligament of Treitz. The small intestine is divided and then a 150 cm roux limb is created and a small bowel anastomosis is completed. No local anesthetic will be utilized in the study patients in order to avoid compounding variable to the assessment of pain scores.

#### **Sleeve Gastrectomy**

Patients having robotic assited sleeve gasterectomy will also be in the study. For this procedure, the same number of trocers and same locations will utilized. The stomach is visualized and fully mobilized. Sleeve gastrectomy is achieved with a linear stapler. The stomach is removed from the 15- mm port site in the right upper quadrant. Similar to the gastric bypass study patients, local anesthesia will not be used to avoid compounding variable in pain assessment.

#### **Port Site Closure**

Either the neoClose® device with provided suture/fasteners or a Carter- Thomason® suture passer with 0 Vicryl will be used to close the port sites. The port sites will be considered closed when no fascial defect can be palpated.

#### **Data Collection**

An autonomous recorder will document the number of sutures required to close each port site as well as the time required to obtain closure during the procedure. A video will be created of each procedure followed by careful analysis of the film by an independent reviewer to record the time of needle exposure to the abdominal cavity as well as depth of needle passage.

Each patient will be placed upon a Dilaudid pain pump immediately after the procedure and transitioned to oral narcotics upon initiation of liquid diet. Analog pain scoring will be completed on each hospital day as well as clinic visits approximately 1,6 weeks and 1 year after the operation. In addition, after patient discharge, the amount of narcotics required during hospitalization will be recorded. An abdominal ultrasound will be completed at 6 weeks and 1 year after the operation to evaluate the incidence of trocar site hernias.

The data will be stored on a password protected UT supplied computer in Excel files by MRN and without names. Upon analysis of the data, the MRN will be deleted thereby erasing all potential patient identifiers.

#### **Data Analysis**

Data will be analyzed using a simple T test within the Excel program as there will be only two groups with a single variable between them. Post Hoc analysis will not be required as with ANOVA secondary to the lack of a third group.

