# SYNOPSIS

Study Title	Randomized Trial Evaluating Effectiveness of neoClose ® Abdominal Closure Device versus CarterThomason ® Needle Passer
Trial Design	A randomized trial intended to compare neoClose ® abdominal closure versus standard Carter- Thomason ® closure in a bariatric surgery gastric bypass and sleeve gastrectomy population. The primary objective of the study is to compare the technical effectiveness of the devices. A secondary outcome will be analysis of pain scores associated with the distinct closures.
	The study will be by a group of 6 Bariatric / General Surgeons at a high volume academic institution. Patients will be randomized upon induction of anesthesia and blinded to the closure technique performed. Video analysis of technical effectiveness will be performed as well as clinic follow up at 1 week ,6 weeks and 1 year after the procedure to assess pain scores. In addition, an abdominal ultrasound will be completed at 6 weeks and 1 year to evaluate the incidence of port site hernia.
Procedure	Both devices will be used to close 12 mm camera and stapler port sites upon completion of a robotic assisted laparoscopic gastric bypass and sleeve gastrectomy. The procedure requires a 12 mm port be placed in the midline approximately 3 cm cephalad to the umbilicus and a second in the right mid abdomen. Port sites will be closed as defined as the inability to palpate a fascial defect .

Study Population	Adults aged 18-70 years with BMI > 35 that have completed a multimodality bariatric workup (EGD, nutrition evaluation and psychological evaluation) and selected to have an elective gastric bypass and sleeve gastrectomy. Subjects who fail to complete extensive pre-operative work up including endoscopic surveillance, nutrition visit, psychological clearance will be excluded from the study. A pregnancy test will be done on female subjects as part of Standard of care. There will be 35 patients per group. A power analysis was completed using the data derived from our preclinical porcine study using primary endpoint of time (32 seconds for Carter- Thomason® and 18.5 seconds for neoClose®). The alpha utilized was 0.05. A total of 70 patients will be screened for the study.

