#### **B. STUDY DESIGN AND PROCEDURE**

#### **Patient Allocation**

This is a randomized study consisting of 35 patients. This site will be the only site across the US doing the study. On the morning of the procedure, qualified subjects who were consented for the study will be randomized to fascial closure with either the neoClose® device or a Carter-

Thomason® suture passer. The floor team and the subjects will be blinded to the closure technique.

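### Hernia and surgical site occurrences have only a t test, which gives no result if neither arm has an event; a count per arm with an exact interval is a cheap improvement

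*Combined protocol and SAP*

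**What the plan says.** Data Analysis is the only section of the combined protocol and SAP that names a method: "Data will be analyzed using a simple T test within the Excel program". It gives as its reason that there are only two groups. No other section names a test, an estimate or a confidence interval.

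Primary Outcome Measure (section D) lists six components. Four are measurements or counts from the closure itself. The other two are surgical site occurrences and the incidence of trocar site hernia on ultrasound. No expected rate is given for either, and site occurrences are not defined.

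Timing differs between sections:

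- **Ultrasound.** The Synopsis (Trial Design) and Data Collection schedule it at 6 weeks and 1 year. The Synopsis (Assessments) names only 6 weeks.
- **Site occurrences.** The Synopsis (Assessments) follows them to 1 year. Adverse Events records port-site events over a shorter period; the wording of its end point is unclear but appears to mean the six-week visit.

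On numbers, the Synopsis says "There will be 35 patients per group", while Patient Allocation says "This is a randomized study consisting of 35 patients".

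**The concern.** A t test needs some variation in the data. For a yes/no outcome with no events in either arm there is none, so the stated analysis is undefined. With small arms and uncommon events that is a realistic outcome.

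The rationale gives lower hernia risk as the reason many surgeons close these ports, and the trial schedules ultrasound to look for hernias. If none is found, the plan can give the two counts but nothing to show how large a difference they leave open. With few events the t test does return a p value, but the plan still asks for no interval.

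**Working it through.** **Inputs.** 35 patients per arm (Synopsis, Study Population); t test as the only method (Data Analysis); two incidences among the primary components (Primary Outcome Measure). Event risks are assumed at 1%, 2%, 3% and 5%.

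**The plan's own figure.** The 35 per group was derived from closure time (32 v 18.5 seconds, alpha 0.05) without a stated SD or power, so it cannot be reproduced. Working backwards at two-sided 5% and an assumed 80% power, SD = 13.5 / ((1.960 + 0.842) × √(2/35)) = about 20.2 seconds. The point here does not depend on this figure, and the sample size was not set for the incidences.

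**Step 1: the t test with no events.** For 0/1 data with n per arm, t = (p1 − p2) / √(s² × 2/n), with s² = [n·p1(1 − p1) + n·p2(1 − p2)] / (2n − 2). At 0/35 v 0/35 both numerator and s² are zero, so t = 0/0. Software returns no statistic and no p value.

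**Step 2: how often this would happen.** With the same risk p in both arms, P(no event in either arm) = (1 − p)^70. If the total were 35, as Patient Allocation says, it would be (1 − p)^35.

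| Assumed risk | 70 patients | 35 patients |
|---|---|---|
| 1% | 49% | 70% |
| 2% | 24% | 49% |
| 3% | 12% | 34% |
| 5% | 3% | 17% |

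**Step 3: what 0/35 v 0/35 leaves open.**

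- Exact unconditional 95% interval for the risk difference (two one-sided score tests at 2.5%, worst case over the unknown common risk): -10.5 to +10.5 percentage points.
- Newcombe interval as a check: the Wilson upper limit for 0/35 is z²/(n + z²) = 3.84/38.84 = 9.9%, which gives -9.9 to +9.9.
- Exact upper limit in one arm: 1 − 0.025^(1/35) = 10.0%.

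The three agree at about 10 points.

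**Step 4: is the t test too liberal for these outcomes?** Enumerating all possible tables at 35 v 35 (68 degrees of freedom, two-sided 5%) gives a true false-positive rate of 0.06%, 0.5%, 1.4% and 3.6% at risks of 1%, 2%, 3% and 5%. It reaches 5.7% at 10%. At low risks the test is conservative.

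**Step 5: missed scans.** If only 28 patients in an arm were scanned (assumed), the upper limit for zero events would be 1 − 0.025^(1/28) = 12.3% instead of 10.0%. The denominator therefore has to be the number scanned.

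**The case against.** The strongest reply is that little is lost. The sections ask for hernia incidence, so 0/35 v 0/35 would be reported whatever the t test does, and no test could find a difference there. The plan makes no equivalence claim, so a reader might infer that it would present an empty test as equal safety, but nothing in the documents says so. The chances of no event rest on assumed risks. At 5% the chance is only 3%, and site occurrences may be commoner than hernias because they could cover several kinds of event. All of this stands, and it limits the point to a missing estimate. It does not supply that estimate.

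Two stronger readings are tempting, and the documents support neither.

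- **False positives from a t test on yes/no data.** Step 4 shows the reverse at low risks, and only a slight excess at 10%.
- **Ports analysed as if they were patients.** Two ports are closed in each patient ("12 mm port in the right mid clavicular line) undergo fascial closure at the completion of the case") and sutures are recorded by port ("An autonomous recorder will document the number of sutures required to close each port site as well as the time required to obtain closure"), so a reader might infer that ports will be entered as separate rows and the error rate inflated. But randomization is by patient ("qualified subjects who were consented for the study will be randomized to fascial closure"), the sample size is in patients, storage is by patient ("The data will be stored on a password protected UT supplied computer in Excel files by MRN and without names"), and the Appendix 1 form has one field for sutures and one for closure duration. No section plans pooling. What is missing is a sentence stating the unit and how the two ports are combined; an inflated error rate would describe an analysis that nobody planned.

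**Conclusion.** The point holds as a cheap improvement to the analysis text. For two of the six primary components, the only named method returns nothing when neither arm has an event, and no interval is planned in any case. The chance of that at 35 v 35 runs from 3% to 49% over assumed risks of 5% down to 1%, and is higher if the total is 35. The quantity left unreported is an uncertainty of about 10 percentage points in either direction, assuming all 70 patients are assessed.

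That the t test fails with no events, and that no interval is planned, is certain from the text. How likely it is to matter depends on risks the documents do not give. The unit of analysis is a minor clarification and is not counted as a harm.

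**What to change.** Add to Data Analysis: 'Trocar site hernia and surgical site occurrences are reported as the number of patients with at least one event over the number assessed (for hernia, the number scanned) in each arm, with an exact 95% confidence interval for the risk difference; the t test is not used for them.'

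Before that sentence can be applied:

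- Name one ultrasound time for the main hernia comparison, after reconciling the Synopsis (Assessments), which gives 6 weeks only, with the Synopsis (Trial Design) and Data Collection, which give 6 weeks and 1 year.
- Define surgical site occurrences and name one window for them, after reconciling the Synopsis (Assessments), which runs to 1 year, with the shorter period in Adverse Events.

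As a minor clarification, add: 'The patient is the unit of analysis; values from the two closed ports are combined into one value per patient.'

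The cost is a few sentences, a little analysis outside Excel for the exact interval, and an interval that will be wide. No p value is needed for these outcomes, so no power is given up to an exact test. For scale, at assumed risks of 2% v 15%, replacing the t test by Boschloo's exact test would lower power from 56% to 41%. Sample size, visits and treatment are unchanged.

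### Bypass and sleeve patients are pooled with no strata described and an unadjusted t test; stratifying by operation and adding one prespecified model term is a cheap gain in precision, not a correction of bias

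*Combined protocol and SAP*

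**What the plan says.** Two operations enter one comparison. Under Small Pouch Gastric Bypass: "Our model will include patients having robotic assisted gastric bypass". Under Sleeve Gastrectomy: "Patients having robotic assited sleeve gasterectomy will also be in the study". Several operators take part: "The study will be by a group of 6 Bariatric / General Surgeons at a high volume academic institution".

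On allocation, the Synopsis says "Patients will be randomized upon induction of anesthesia and blinded to the closure technique performed", while Patient Allocation places randomization on the morning of the procedure. Neither mentions strata or blocks. Both times come after the operation has been scheduled (section E, Patient Population), so operation is available as a stratum.

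The Data Analysis section is the whole analysis plan: a t test for the data in general, chosen "as there will be only two groups with a single variable between them", with no covariate. The Synopsis sizes the trial on closure time ("A power analysis was completed using the data derived from our preclinical porcine study using primary endpoint of time") and states "There will be 35 patients per group". Patient Allocation states "This is a randomized study consisting of 35 patients".

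**The concern.** If operation predicts an outcome, an unadjusted comparison carries that variation as noise. A prespecified term removes it for one degree of freedom. The Data Analysis section allows no covariate, so an adjustment made later would be post hoc. What is at stake is precision on closure time and on the other continuous outcomes (needle time, depth, pain scores).

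Two related gaps sit in the same section. A t test does not suit the binary outcomes listed under Primary Outcome Measure (surgical site occurrences, hernia). The unit of analysis is also not named. Section B, Data Collection, records sutures for each port site, while the Appendix 1 form has one closure-duration field and one suture field per patient, and no field for operation.

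**Working it through.** **The plan's own figure.** The inputs are 32 s v 18.5 s (difference 13.5 s), alpha 0.05 and 35 per group, all from the Synopsis. SD, power and sidedness are not given, so 35 cannot be reproduced. Solving n = 2(z_alpha/2 + z_beta)² SD² / 13.5² = 35 for SD, two-sided:

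- 80% power: SD = sqrt(35 × 182.25 / (2 × 7.849)) = 20.2 s
- 90% power: SD = sqrt(35 × 182.25 / (2 × 10.507)) = 17.4 s

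Baseline power is therefore an assumption, and both values are carried below.

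**Is there bias?** No. The expected imbalance in operation under randomization is zero. In 10,000 simulated unstratified trials of 70 per scenario, the bias of the unadjusted difference was at most 0.003 SD (simulation noise) and type I error was 5.0 to 5.2%.

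**Chance imbalance in a single trial** (hypergeometric, sleeve share assumed 40 or 50%). With 35 v 35, the probability of a difference of 20 points or more in sleeve share is 0.087 (28 sleeves) or 0.151 (35 sleeves). The shift this causes is 0.20 × sqrt(R2 / (s(1-s))), where s is the sleeve share and R2 is the share of variance due to operation. At s = 0.5:

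- R2 = 5%: 0.20 × sqrt(0.05/0.25) = 0.09 SD
- R2 = 10%: 0.20 × sqrt(0.10/0.25) = 0.13 SD

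The standard error is sqrt(2/35) = 0.239 SD, so these shifts are about 0.4 and 0.5 of a standard error. The t test's error rate already allows for them.

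**Effect of the model.** With arms balanced on operation, the standard-error ratio of device + operation to the t test is sqrt((1-R2)(N-2)/(N-3)). Power is from the noncentral t, two-sided 0.05, N = 70, with effects of 0.679 SD (80% baseline) and 0.786 SD (90% baseline).

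| Assumed R2 | SE ratio, N = 70 | Power from 80% | Power from 90% | SE ratio, N = 35 |
|---|---|---|---|---|
| 0 | 1.007 | 80% | 90% | 1.016 |
| 5% | 0.982 | 82% | 91% | 0.990 |
| 10% | 0.956 | 84% | 93% | 0.963 |
| 20% | 0.901 | 88% | 95% | 0.908 |

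Break-even R2 is 1/(N-2): 1/68 = 1.5% with 70 patients and 1/33 = 3.0% with 35.

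**Strata without the model.** Stratifying removes the operation component from the true variance of the difference, but the t test still estimates it. Its standard error is too large by about 1/sqrt(1-R2). In simulation with balanced strata, type I error is about 0.044, 0.039 and 0.028 at R2 of 5, 10 and 20%. The model stays at its nominal level, and nearly all of the power gain comes from it.

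**The case against.** The strongest reply is that the plan contains no error here. The t test is valid, and no passage says that operation affects closure time. The Sleeve Gastrectomy section gives the same number and locations of trocars as for bypass, which suggests a small operation effect. Below break-even the change costs precision. All of this stands, and it is why the point is an optional improvement.

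A reader might infer that pooling confounds the device comparison, or that the t test is invalid because patients differ by more than one variable. The documents support neither. Device is randomized, and in context the single-variable remark explains why a t test is used and not an ANOVA. With only two arms, that is a fair description.

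A reader might also take the 15 mm extraction port, which appears only in the Sleeve Gastrectomy section, as proof that the operations differ in closure time. It is not proof, because no passage says whether that port is closed or timed. It does show that the closure outcome must be defined before any model is fitted: a sum over two port times cannot be prescribed until this is settled.

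The Rationale's remark on variation concerns the operator (a technique that is hard to learn), and strata by operation do not balance surgeons. A surgeon random effect, or robust standard errors for suture counts, may be considered. Neither is part of this point.

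**Conclusion.** The point holds as a low-severity gain in precision. Operation is known before randomization, no strata are described, and the planned test leaves any variance due to operation in the error term. No gain is demonstrated, because operation mix, SD, power and operation effect are all absent from the documents. Over assumed R2 of 0 to 20% with 70 patients, the standard error moves between +0.7% and -10%, and power rises by 0 to 8 points from an 80% baseline or 0 to 5 points from 90%. If the total is 35, the standard error moves between +1.6% and -9%. For closure time the true value may lie near the low end. The trade is still favourable: the loss is capped at 0.7% (1.6% with 35 in total), and the break-even R2 is low.

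**What to change.** 1. **Reconcile first.** Settle 35 per group (Synopsis) against 35 patients (Patient Allocation). Settle which port sites are closed and timed in each operation (Synopsis, Small Pouch Gastric Bypass, Sleeve Gastrectomy). Settle per-port recording (section B, Data Collection) against the single duration field in Appendix 1.
2. **Patient Allocation.** Stratify by scheduled operation (bypass, sleeve) with concealed permuted blocks of randomly varying size, for example 4 or 6. Operators at this single site see the device, so fixed blocks could be guessed.
3. **Data Analysis, continuous outcomes.** For closure time and the other continuous outcomes, replace the t test with a prespecified linear model of device + operation, using one defined value per patient. Adopt this together with step 2.
4. **Data Analysis, binary outcomes.** For surgical site occurrences and hernia, report a risk difference stratified by operation (for example Mantel-Haenszel) in place of a t test. The documents give no event rates, so its precision is not assessed here.
5. **Appendix 1.** Add a field for operation, completed before the MRN is deleted.

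The cost is one degree of freedom, two randomization lists and one form field, with no extra patients or visits. Incomplete last blocks of up to 6 could leave the arms at worst 38:32, which raises the standard error by sqrt((1/38 + 1/32)/(2/35)) - 1 = 0.4%.

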Assessments	
 
The study will allow for the evaluation of technical effectiveness and analysis of pain scoring:
 
Technical Effectiveness 
 
Number of sutures required to complete closure.
 
Time required to complete closure.
 
Depth of needle penetration to complete closure.
 
Evaluate for surgical site occurrences immediately post op as well as at 1 ,6 weeks and 1 year after closure procdure.
 
Evaluation for port site hernia at 6 weeks with abdominal ultrasound.
 
 
 
Pain Evaluation 
 
Visual analog pain scale will be used to assess pain at both port sites.
 
Amount of intravenous narcotics required during hospitalization.
 
Hospital stay duration.
 
 
 
The study will allow for assessment of pain scores during hospitalization and at follow up visits approximately 1 week ,6 weeks and 1 year.
 

Data Collection	During the procedure, an independent examiner will record the amount of time and number of suture passes to obtain port site closure. In addition, an independent review of video from each procedure will be completed to record the time and depth of needle exposure. Patients will fill out pain analog scores

	during hospital stay and follow up visits. Care givers on the floor and in clinic will
	be blinded to the closure technique.
	Hospital records will be reviewed to record narcotic requirements.

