#### A. RATIONALE

Laparoscopic surgery requires the utilization of multiple ports with varying diameters. In the bariatric population, gastric bypass and sleeve gastrectomy requires 12 mm port placement for camera and stapler insertion. Many surgeons favor closure of the fascial defect in order to decrease the risk of hernia occurrence. Various type of port closure is available. The most popular closure device is the Carter-Thomason® needle. This device has inherent limitations:

(1) Insertion of the needle is associated with injury to the viscera and blood vessels.

(2) The width of the suture placed using the Carter-Thomason® needle can lead to compression of peritoneum and entrapment of underlying nerves, causing post-operative port site pain.

(3) Placement of the suture is challenging in the obese patient. 

Very few studies have been completed to compare novel devices to the Carter- Thomason® with equivocal data.  $^{(2)(3)}$ 

Current practice requires fascial closure with a suture passing needle which passes the suture material through some amount of subcutaneous tissue, muscle, and fascia. This technique is often associated with elevated levels of discomfort which can remain weeks after the operation is complete. In addition, the technique of port site closure can be difficult to learn leading to prolonged times potential needle exposure to underlying viscera as well as times for port site closure.

The development of a novel closure device which relies upon the guided deployment of suture / fasteners could help improve the learning curve associated with port site closure. In addition, such a technique that would not require passage of suture material through adjacent muscle and isolated the posterior fascia could lead to an improvement in patient satisfaction secondary to a decrease in pain.

The neoClose ® device is an abdominal closure device that has been approved by the FDA in 2013 (510K) to use as such. The study aims to add to the existing knowledge about these kinds of devices and also to evaluate the effectiveness of the neoClose® device compared to the Carter-Thomason® device. Moreover, surveys will also be administered to patients using the Visual Analog Scale of pain to establish pain scores associated with individual closures.

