# **Secondary Outcome Measures**

- Comparison of perioperative and post operative pain via visual analog scoring while in the hospital and at follow up appointments 2,6 weeks and 1 year after discharge.
- Comparison of narcotic requirements during hospitalization.
- Comparison of hospital stay duration.

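### Pain is scored repeatedly and at two ports, but the plan names no main pain result and offers only a simple t test, which leaves false-positive control and use of the repeated scores open

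*Combined protocol and SAP*

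**What the plan says.** The Synopsis gives pain secondary status: "A secondary outcome will be analysis of pain scores associated with the distinct closures". Its Assessments row adds that "Visual analog pain scale will be used to assess pain at both port sites". Section B, Data Collection, sets the timing: "Analog pain scoring will be completed on each hospital day as well as clinic visits approximately 1,6 weeks and 1 year after the operation". Section D, Secondary Outcome Measures, lists the same comparison but places the clinic scores at "follow up appointments 2,6 weeks and 1 year after discharge", so the first visit is at 1 week in the Synopsis and Data Collection and at 2 weeks here.

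The analysis plan is two sentences in section B, Data Analysis. The first begins "Data will be analyzed using a simple T test within the Excel program as there will be only two groups with a single variable between". The second is "Post Hoc analysis will not be required as with ANOVA secondary to the lack of a third group". The only error level stated is in the Synopsis: "The alpha utilized was 0.05", given for the sample size calculation on closure time.

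Neither document part names a main pain time point, a way to combine visits or ports, a longitudinal model, a rule for missed visits, or any control of repeated testing. The two data forms in Appendix 1, as extracted, each show one pain scale with no port label.

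**The concern.** A two-sample t test takes one value per patient. Pain yields several: one for each hospital day and clinic visit and, if the Synopsis is followed, one for each port. The analyst must therefore test each occasion separately or form a summary that the plan does not define. Separate tests inflate the chance that some visit or port shows a nominally significant difference. A summary chosen once the data are known is open to selection.

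The number of groups does not settle this, because the repetition comes from visits and ports.

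The Rationale rests much of its case for patient benefit on pain, saying of the current technique: "This technique is often associated with elevated levels of discomfort which can remain weeks after the operation is complete". Pain has no power calculation of its own, so what can be learned about it depends on how efficiently the repeated scores are used.

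**Working it through.** **The plan's own figure.** The plan states no family-wise error rate and no power for pain. Its only calculation is 35 per group, from closure times of 32 and 18.5 seconds (difference 13.5) at alpha 0.05. The SD and power are not given, so it cannot be reproduced. Back-solving with two-sided testing, SD = 13.5 / ((1.960 + 0.842) × √(2/35)) = 20.2 seconds at 80% power, and 17.4 seconds at 90%. Neither bears on pain.

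**Inputs for pain.**
- Clinic visits: 3 (Data Collection). The 1-week or 2-week conflict does not change the count.
- Hospital days: not stated; 1 to 3 assumed. This gives 4 to 6 occasions.
- Ports: 2 (Synopsis), or one score per visit (Appendix 1 forms as extracted).
- Alpha: 0.05, two-sided assumed.
- Patients: 35 per group (Synopsis). Section B, Patient Allocation, describes 35 patients in the study; the Synopsis figure is used here.
- Correlations between scores: not in the documents; a range is shown.

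**Chance of at least one false positive if each score is tested separately.** For m independent tests it is 1 − 0.95^m: m = 8 gives 0.337, m = 10 gives 0.401 and m = 12 gives 0.460. For correlated scores it was simulated (20,000 trials, 35 per arm, t tests at 0.05) with constant correlation over time and between ports. The correlation across both is the product of the two.

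| Occasions × ports | Tests | Independent | Time 0.3, port 0.5 | Time 0.5, port 0.7 | Time 0.7, port 0.8 |
|---|---|---|---|---|---|
| 4 × 2 | 8 | 33.7% | 30.2% | 24.8% | 19.2% |
| 5 × 2 | 10 | 40.1% | 35.2% | 29.2% | 22.7% |
| 6 × 2 | 12 | 46.0% | 40.0% | 32.9% | 24.7% |
| 4 × 1 | 4 | 18.5% | 17.2% | 15.6% | 13.0% |
| 5 × 1 | 5 | 22.6% | 21.6% | 18.4% | 15.0% |
| 6 × 1 | 6 | 26.5% | 23.9% | 20.8% | 17.0% |

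In the single-port rows only the time correlation applies.

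**Gain from averaging the first two clinic visits.** The variance of a mean of two scores, relative to one, is (1 + ρ)/2.
- ρ = 0.5: 0.75, a 25% cut.
- ρ = 0.7: 0.85, a 15% cut.

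With 35 per arm, the difference detectable with 80% power at one visit is 0.68 SD (0.679 from the t distribution; 2.8016 × √(2/35) = 0.670 by normal approximation). Averaging lowers it to 0.679 × √0.75 = 0.59 SD at ρ = 0.5, or 0.679 × √0.85 = 0.63 SD at ρ = 0.7. This assumes equal effect and SD at both visits.

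**When averaging loses.** Let the effect be δ₁ at the first visit and δ₂ at 6 weeks, with equal SDs. Averaging beats a first-visit test when (δ₁ + δ₂)/2 ÷ √((1 + ρ)/2) exceeds δ₁, that is, when δ₂/δ₁ > 2√((1 + ρ)/2) − 1.
- ρ = 0.5: 2 × √0.75 − 1 = 0.73.
- ρ = 0.7: 2 × √0.85 − 1 = 0.84.

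If the effect has gone by 6 weeks, the first-visit difference needed at ρ = 0.5 is 2 × 0.588 = 1.18 SD instead of 0.68 SD.

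**The case against.** The strongest reply is that the plan does not say it will test every score separately. It names a method and is silent on how pain scores enter it. A t test on each patient's mean score is valid, fits in Excel, and gives the same efficiency gain as calculated above when no visit is missed. This stands: separate testing is an inference, and a mixed model is not the only remedy. But a summary that is not named in advance leaves the same freedom to choose.

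The sentence about a third group is also correct for what it covers, namely pairwise comparisons after ANOVA. A reader might infer that it denies any multiplicity problem in the trial; it does not say so. The gap is that nothing else in the plan covers visits and ports.

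A reader might further infer that a chance finding is likely. The figures do not support that. Even independent tests reach only 46% at 12, and pass one half at 14 (1 − 0.95^14 = 0.512). Scores from one patient are correlated, which lowers the figure. Nor are the repeated scores simply wasted if tested visit by visit: the loss depends on the correlation and on how steady the effect is.

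Finally, the count of tests is uncertain, because the forms suggest one score per visit, and pain is secondary, so the primary comparison is untouched. Both points stand. They limit the size of the problem but do not remove it.

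**Conclusion.** The gap is real and of moderate weight. Repeated, correlated pain scores have no named main result, no combining rule and no repeated-measures analysis, and the two-group argument does not fill that gap. If scores were tested separately, the nominal 5% would become about 19% to 46% with two ports, or 13% to 26% with one score per visit. False-positive risk is substantially inflated but stays below one half. These ranges rest on 1 to 3 hospital days, two-sided tests, no true effect, and time correlations from 0 to 0.7.

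Naming one averaged result holds the error at 5% for that claim. The precision gain of 15% to 25% in variance depends on correlation 0.7 to 0.5 and on equal effect and SD at the two visits.

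**What to change.** In section B, Data Analysis:

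1. Name one pain result: the device difference averaged over the first two clinic visits, with the two port scores averaged per patient. This matches the Rationale's interest in pain lasting weeks.
2. Estimate it from a repeated-measures mixed model of the clinic scores with device, visit and device-by-visit terms, which keeps patients who miss a visit. The minimal version is a t test on each patient's mean score, with a stated rule for missed visits.
3. Report hospital-day, single-visit, single-port and 1-year results as estimates with confidence intervals and no claim of significance.
4. The third-group sentence may stay if it is limited to comparisons among groups.

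Reconcile the timing of the first clinic visit between the Synopsis and Data Collection (1 week) and Secondary Outcome Measures (2 weeks). Make clear on the Appendix 1 forms whether pain is scored per port.

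The cost is one paragraph of text, a form clarification, and software other than Excel for the full version. No patients, visits or measurements are added. The price is dilution of an effect confined to one visit or port: at correlation 0.5, averaging beats a first-visit test only if the 6-week effect is at least about 73% of the first-visit effect.
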